Randomized, double-blind, placebo controlled study on the effect of a single postoperative administration of low dose ketamine after gastric bypass and gastrectomy surgeries

Primary Investigator: [name]. Ph.D.

New York University Langone Medical Center, Department of Anesthesiology

Study Number: S13-00719

Background

Bariatric surgeries for the treatment of obesity and type II diabetes represent one of the most common abdominal operations, with over 300,000 cases performed in 2011.¹ Postoperative care is a critical component for outcome from these procedures. Optimal postoperative pain management, however, can be difficult to achieve. While many incisions are small, a significant proportion of patients who undergo bypass or sleeve gastrectomy still stay in the hospital for more than two to three days, and patients can suffer from a combination of incisional and visceral pain. Pain control currently is achieved through a combination of opioids, Acetaminophen, and NSAIDs. Opioids are the most powerful analgesic in this group. Opioids, however, are well known to cause sedation and respiratory depression, which can significantly impact respiratory status of bariatric patients, many of whom already suffer from respiratory compromise due to obesity and obstructive sleep apnea. NSAIDs, meanwhile, may increase the rate of bleeding complications. Thus, additional analgesics are needed to achieve optimal pain control.

A key component of postoperative pain experience is depressed mood, which further complicates functional recovery.^{2,3} Bariatric patients, in particular, have a high co-morbidity of depression, which can be worsened by postoperative pain.⁴⁻⁶ Optimal pain control, on the other hand, has been shown to improve patient satisfaction, elevate mood, and allow early participation in physical rehabilitation such as early mobility, all of which contribute to better surgical outcome. Studies are needed, however, to examine additional postoperative measures that can enhance functional recovery in bariatric patients.

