Ketamine, given for postoperative pain control, can be hypothesized to have long lasting analgesic effects as well as effects on improving mood and function in the postoperative period. Ketamine can be administered as a single dose in the post-anesthetic care unit (PACU), where patients are closely monitored for potential side effects. We hypothesize that postoperative use of ketamine should lead to improvement in pain indices including visual analog scale (VAS), a decrease in opioid requirement, mood improvements as measured by psychometric indices, and finally improvements in functional measures including early mobility and faster discharge from the hospital. In addition, we will assess serum levels of IL-1, 6, TNF- α , and BDNF to see if alterations in levels of cytokines and neurotrophic factors occur with postoperative pain and how ketamine treatment may influence the levels of these biomarkers.

Study Objective

Specific aim 1: examine the effect of a single, subanesthetic dose (0.4mg/kg) of ketamine vs. saline control on mood and postoperative function in patients who have undergone gastric bypass and sleeve gastrectomies.

Pain relief and changes in postoperative mood and function will be assessed using both patient report, in the forms of a series of questionnaires, and medical chart review. The questionnaires we use will be Beck Depression Inventory (BDI), Visual Analog Scale (VAS), McGill's short form, QoR-15 form and the Montgomery-Asberg Depression Rating Scale (MADRS). Please see below for a detailed discussion of these forms. In addition, from the chart review we will monitor length of stay during hospitalization, opioid usage per hour during the PACU stay before and after ketamine infusion, total opioid usage per day throughout the hospital stay, time to out of bed to chair, and spirometry use after ketamine infusion.

Specific aim 2: examine the effect of a single, subanesthetic dose (0.4mg/kg) of ketamine vs. saline control on inflammatory cytokines and neurotrophic factors in the postoperative period.

We will examine the effect of ketamine on proinflammatory markers and neurotrophic factors known to be linked with pain. We will examine levels of interleukin factor 1 and 6 (IL-1, IL-6), TNF- α , and BDNF. This aim will provide potential mechanism of action for ketamine.

Overall study design and plan

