This is a randomized, double-blind, placebo-controlled, two-arm parallel, single-center study. One hundred subjects (50 in each arm) will be enrolled. Subjects, between the ages 18 and 65, undergoing laparoscopic gastric bypass or sleeve gastrectomy under general anesthesia will be screened for eligibility to participate in the study. Subjects will be screened, recruited and consented during the preadmission visit prior to surgery. Eligible subjects will be randomized to one of the two treatment group in a 1:1 ratio to receive either IV ketamine (0.4mg/kg) or matching placebo. Both men and women will be recruited, and there is no limitation as to racial and ethnic origin.

Participation in the study will not alter the patient's surgical or anesthetic care, post-anesthetic care, or care on the floor. In the PACU, patients, if deemed medically stable by the study physician, will receive either 0.4mg/kg IV ketamine or placebo. All patients will also receive standard post-anesthetic monitoring and care, as well as routine care after transfer out of the PACU. There is no restriction on the use of other analgesics throughout the hospital stay. Patients are followed until the date of discharge, and endpoints (see below) are collected from patient reports as well as from medical charts. During their hospital stay (and once after their discharge from the hospital), patients will fill out five questionnaires which provide estimates of their postoperative pain control, mood and function, and quality of postsurgical recovery.

Patients will be randomized using a block randomization code for assigning 100 subjects to two groups. In Excel we generated 100 random numbers. In the next column we inserted multiple copies of the sequence PCPC where p= "placebo" and c = "control", forming 25 blocks. Then we sorted the random numbers in each 4 subject block, including the assignment letters (P, C) in the sort. The remaining list of Ps and Cs is the randomization.

To check the balance, we then did running counts of the cumulative repeats of "p" and "c" and "p - c". The tally for each totaled 50 and the two groups were always within 2 counts of being perfectly balanced, which met our goal. The list can be extended at will to accommodate screening failures.

Randomization lists will be sent to the pharmacy who will then be able to distribute the study drug/placebo as patients are enrolled and undergoing surgery, and the remainder of the study staff will be blinded.

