An additional component of the study, which is entirely optional, is to obtain patient serum samples (about two teaspoons) in the operating room and 15 minutes and 4 hours after ketamine infusion. We will use these samples to assess levels of IL-1, IL-6, TNF- α , and BDNF, which are markers for pain. In addition, with patient consent, we will also store serum samples for future research use to measure other cytokines and neurotrophic factors and molecular markers associated with pain and depression.

Study site: Tisch Hospital

Outcome measures

Primary outcome measure: scores on the following questionnaires: 1) The Beck Depression Inventory (BDI); 2) Visual Analog Scale (VAS) score; 3) McGill's short form; 4) QoR-15 form; and 5) Montgomery-Asberg Depression Rating Scale (MADRS). The BDI and MADRS provide assessments for mood and function, VAS and McGill's assess pain, and QoR-15 assesses patient's overall satisfaction with postoperative recovery.

After consent is achieved in the pre-admission clinic prior to surgery, patients will be asked to fill out BDI, MADRS and QoR-15 forms to establish baseline scores. The BDI, MADRS will be filled out on postoperative days (POD) 0 after the infusion of ketamine, and BDI, MADRS and QoR-15 forms will be repeated on POD1, 2 and 7. McGill's short form will be filled out prior to discharge from the PACU and on POD 1, 2 and 7. VAS will be filled prior to PACU discharge, and every day while patient is in the hospital and on POD 7. VAS is a routine part of hospital care and will be administered daily whether a patient is enrolled in the study or not. If a patient has been discharged prior to POD2 or 7 (patients typically are discharged on POD2 or 3 in our practice), then a member of the study team will contact the patient by telephone to fill out these questionnaires.

Secondary outcome measures: 1) length of stay during hospitalization; 2) opioid usage per hour during the PACU stay before and after ketamine infusion; 3) opioid usage per day throughout the hospital stay; 4) time to out of bed to chair (OOB); 5) spirometry use 4 hours after the termination of ketamine infusion; 5) anti-emetic use in the PACU.

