Length of stay, opioid usage, and anti-emetic use will be recorded from electronic medical chart. Patient will be asked to record and report the time to OOB. Spirometry use will be assessed by a study team member to determine whether the patient is meeting the goal set by the surgical team 4 hours after ketamine infusion.

Exploratory secondary outcome measures: changes in serum levels of IL-1, IL6, TNF- α , and BDNF, which will be collected at baseline (in the OR preoperatively), and 15 min and 4 hours after the termination of ketamine infusion.

Study population

Inclusion criteria:

1. Adults, >18 years, <65 years, who will undergo gastric bypass or sleeve gastrectomy.
2. Subject is non-lactating and is either:
 - a. Not of childbearing potential; or
 - b. Of childbearing potential but is not pregnant at time of baseline as determined by pre-operative pregnancy testing.
3. Subject is ASA physical status 1, 2, or 3.
4. Subject who is deemed medically stable

Exclusion criteria:

1. <18 years of age; >65 years of age
2. Pregnant or breastfeeding
3. Does not speak or understand English (the study forms used are copy-right in English)
4. Cognitively impairment (by history) or clinical signs of altered mental status
5. History of misuse or abuse of ketamine
6. History of chest pain or chest pain in the PACU
7. Use of a medication that interferes with metabolism of ketamine within the last 24 hours
8. A diagnosis of schizophrenia and/ or a history of chronic antipsychotic medication use
9. History of head trauma
10. History of intracranial mass or hemorrhage
11. History of stroke
12. History of cardiac arrhythmia
13. Subject for whom ketamine is contraindicated
14. Unwillingness to give informed consent according to HIC guidelines

Entry into Study

Flyers will be designed and posted in the bariatric clinic as well as the pre-admissions testing (PAT) clinic to inform patients about this study. Patients will be recruited from the bariatric clinic during their visit with the pre-surgical clinic visit with their surgeons, from the PAT during their preadmission visit, or from the holding area on the day of surgery. Researchers will hold a general discussion with interested patients regarding the study. The patient may have family included, if he/she prefers. We will be approaching all subjects (male and female) who are undergoing laparoscopic gastric bypass or sleeve gastrectomy.

Pre-Study Screening

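### Daily opioid use is recorded only until discharge, which ketamine is hypothesised to hasten, and no common window is set, so comparisons that include POD2 or later are open to selection bias

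*Combined protocol and SAP*

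**What the plan says.** - **Outcome.** Outcome measures, Secondary outcome measures, item 3: "opioid usage per day throughout the hospital stay". Specific aim 1 under Study Objective has the same restriction: "total opioid usage per day throughout the hospital stay".
- **Source.** Later in Outcome measures: "Length of stay, opioid usage, and anti-emetic use will be recorded from electronic medical chart".
- **Follow-up.** Overall study design and plan: "Patients are followed until the date of discharge". For patients who have already left by POD2 or POD7, "then a member of the study team will contact the patient by telephone to fill out these questionnaires". That call covers the questionnaires. Opioid use is not part of it.
- **Time of discharge.** Outcome measures: "patients typically are discharged on POD2 or 3 in our practice". The Background adds that a sizeable share of patients "still stay in the hospital for more than two to three days", without a percentage.
- **Hypotheses.** Study Rationale expects lower opioid need with ketamine and "finally improvements in functional measures including early mobility and faster discharge from the hospital". Length of stay is itself secondary outcome 1.
- **Analysis.** Both Statistical Analysis sections name repeated-measures ANOVA for the outcome measures, with rank tests for non-normal data. Neither gives a window for opioid use or a rule for days after discharge. Neither says whether opioid use is compared by day, averaged or totalled.

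**The concern.** Randomisation makes the arms comparable as a whole. It does not make the patients still in hospital on POD2 or POD3 comparable, because leaving is a post-randomisation event that the protocol itself expects treatment to change. If patients with low opioid need tend to go home first, and more of them do so on ketamine, those who remain on ketamine are the more strongly selected high-need group. Their mean opioid use then looks too high relative to placebo.

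Reduced opioid need is a named hypothesis, and the Background gives opioid sedation and respiratory depression in bariatric patients as a reason to look for additional analgesics. As planned, success on length of stay could partly hide success on opioid sparing.

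**Working it through.** **The plan's own figure.** No size or SD is stated for opioid use. The only power figure concerns the psychometric measures (difference 22.5%, SD 40%, alpha 0.05, power 0.80). It reproduces with a two-sided test: n = 2 × (1.960 + 0.842)² × (40/22.5)² = 49.6, so 50 per arm. It does not bear on the selection problem, but it supplies a reference effect of 22.5/40 = 0.5625 SD.

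**Is the problem confined to one way of analysing the data?** The plan leaves several readings open.

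1. Day by day among patients present: selected from about POD2 onward.
2. Repeated-measures ANOVA on complete cases: patients discharged early drop out of every day, so POD0 and POD1 are affected too.
3. Average per day of stay: with an assumed course of 30, 20, 10, 5 units, a 3-day stay averages (30+20+10)/3 = 20.0 and a 4-day stay 65/4 = 16.25. The shorter stay looks worse on the same course.
4. Total over the stay, which departs from the per-day wording: the same course gives 60 against 65, so the shorter stay looks better.

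Each reading mixes opioid use with length of stay.

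**Size for the day-by-day reading (all inputs assumed).** Let POD1 and later-day need have SD 1 and correlation r, with ketamine lower by d on both days. A patient is still in hospital on the later day if c × (POD1 need) + √(1 − c²) × (independent noise) exceeds a cut-off that keeps a chosen share of placebo patients. Here c is the need-discharge correlation. With λ(a) = φ(a)/[1 − Φ(a)] and half of placebo still in hospital:

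observed reduction = d − r × c × [λ(c·d) − λ(0)], where λ(0) = 0.7979.

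For d = 0.30 and r = 0.5 or 0.7:

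| c | λ(c·d) | Ketamine in hospital | Bias (SD) | Attenuation |
|---|---|---|---|---|
| 0 | 0.7979 | 50% | 0 | 0 |
| 0.3 | 0.8560 | 46% | 0.009; 0.012 | 2.9%; 4.1% |
| 0.6 | 0.9159 | 43% | 0.035; 0.050 | 11.8%; 16.5% |
| 1 (POD1 need decides) | 0.9982 | 38% | 0.100; 0.140 | 33%; 47% |

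Example, c = 1 and r = 0.5: 0.5 × (0.9982 − 0.7979) = 0.100, so 0.200 SD is seen instead of 0.30.

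For d = 0.56 and c = 1, λ(0.56) = 1.1853. The observed reduction is 0.56 − 0.5 × 0.3874 = 0.366 SD (r = 0.5) or 0.56 − 0.7 × 0.3874 = 0.289 SD (r = 0.7), a loss of 35 to 48%.

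If 90% of placebo are still in hospital, the placebo term is λ(−1.2816) = 0.1950. For d = 0.30 the ketamine term is 0.2221 (c = 0.3) or 0.2515 (c = 0.6). Attenuation is then r × c × (difference)/0.30 = 1.4 to 1.9% or 5.7 to 7.9%.

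**Direction.** A second simulation correlated later-day need directly with still being in hospital.

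- No true opioid effect, 50% of placebo and 30 to 40% of ketamine patients in hospital: ketamine appears worse by 0.05 to 0.11 SD (correlation 0.3) or 0.10 to 0.21 SD (0.6), and by nothing at correlation 0.
- True reduction 0.25 SD, ketamine prolonging stay (probit shift 0.4): the observed reduction is 0.31 to 0.34 SD, so the bias favours ketamine by 0.06 to 0.09 SD.

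**Precision.** Fewer patients remain on later days. Power is Φ(0.5625 × √(n/2) − 1.96): 0.80 with 50 per arm and 0.51 with 25, before any attenuation.

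**The case against.** The strongest reply is that the documents do not state the analysis being criticised. They define what is measured and name a family of tests. A reader might infer that the plan tests each day among in-hospital patients and will therefore understate ketamine's effect. The text does not support that. The day-by-day test is an inference, faster discharge is only a hypothesis, and the documents give no discharge criterion and no link between opioid need and going home. This part of the objection stands, and it makes the direction conditional.

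The large figures are also open to attack. Attenuation of 33 to 47% requires POD1 need alone to decide discharge, with half of placebo already gone on the day compared. That fits POD3 better than POD2, given that discharge is typically on POD2 or POD3. This stands too: those figures are the upper end of a range.

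Finally, this is one of six secondary outcomes. PACU opioid use per hour is collected before any discharge, POD0 and POD1 use should be largely intact when compared by day, and a difference in length of stay would be visible because it is reported. All true, and it limits the consequences. It does not remove the problem, because every reading the plan leaves open mixes opioid use with length of stay once POD2 or later is included.

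**Conclusion.** The concern holds in conditional form. Opioid use stops being observed at discharge, discharge is expected to respond to treatment, and the plan has neither a common window nor a rule for the days after. Comparisons that include POD2 or later are therefore not comparisons of the randomised groups.

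For the day-by-day reading, the bias runs against ketamine if both the faster-discharge hypothesis and a link between lower need and earlier discharge hold. It is zero without the link and reverses if stay is prolonged. The documents fix neither its direction nor its size. With half of placebo still in hospital, the illustrated attenuation runs from about 3% to 47%, and the top of that range needs an extreme discharge rule. Partial need-discharge links of 0.3 to 0.6 give about 3 to 16.5%. The primary outcomes and the sample size are not affected.

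**What to change.** Make the tested opioid outcome the cumulative use from end of infusion through the end of POD1, compared between arms in all randomised patients. Given the usual discharge on POD2 or POD3, nearly all patients should still be in hospital over that window. State in advance the rule for anyone who leaves before it closes and the starting time for anyone randomised but not infused. Report POD2 and later descriptively, with the number in hospital per arm on each day, alongside length of stay.

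This needs only a change of wording in the analysis section and uses the same chart data. The small downside is that use on POD2 and later is no longer tested. If the investigators want to keep those days, opioid use could be asked about at the POD2 and POD7 contacts already planned, at the price of extra data collection and of combining patient-reported with charted use.

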Sample Size Justification: Previous studies on the antidepressant effects of ketamine on depressed patients typically yield a mean difference in psychometric measures of 40%, with a standard deviation of roughly 40% as well. Power analysis yields $n = 50$ patients in each arm. This will allow for us to detect a true difference in the mean value of our outcome variable of $\pm 22.5\%$ with a probability (power) of 0.8. The type I error probability associated with this test of the null hypothesis that the population means of the ketamine versus control groups are equal is 0.05.

Statistical Analysis: For this study, descriptive statistics will be performed for all data and subgroups as needed:

- 1) Outcome tests (see above), N (%) for each category, showing absolute values, absolute

and percent differences, stratified by treatment etc.

- 2) Demographics showing continuous parameters (age, height, weight, etc.) as mean + SD; categorical parameters, as N (%); all also stratified by treatment.

Analysis of variance (ANOVA) test with repeated measures will be performed to determine within-patient effects (time) and between patient effects (treatment) on outcome measures. Pearson correlation will be used to assess relationships between continuous variables, and Spearman's Rho will be used for ranked data. For non-normally distributed, the Kruskal-Wallis test will be used for global significance, and Mann Whitney for subsequent pairwise comparisons.

Exploratory analysis will fit continuous (VAS score, length of stay in the hospital) and categorical (ordinal outcome data) to a Logistic Regression model which predicts the treatment bivariate (IV ketamine or placebo).

Interim Data analysis: An interim data analysis will be performed after a total of 50 patients have completed the study. An analysis of primary and secondary endpoints will be analyzed, and if the primary endpoints are met, we will opt to terminate the study.

DATA SAFETY AND MONITORING PLAN

Timeline

- 1) Estimated start date: Sept 1, 2013
- 2) Estimated time for start-up: 2 months
- 3) Time allotted for enrollment: 2 years
- 4) Estimated study end date: August 30, 2015

Data acquisition and management

The research material obtained from human subjects in this proposed study will be collected solely for research purposes. It will be as follows:

- a. *Clinical information* obtained by medical history, questionnaires and interviews.

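### The secondary spirometry outcome is scored only as goal met or not met, against an undefined goal; recording the achieved value and the goal would avoid losing roughly a third to two thirds of the information

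*Combined protocol and SAP*

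**What the plan says.** Specific aim 1 (Study Objective) lists, among the items taken from chart review, "time to out of bed to chair, and spirometry use after ketamine infusion", with no scale or unit. The secondary outcome list under Outcome measures names "spirometry use 4 hours after the termination of ketamine infusion". The paragraph after that list gives the only definition: a study team member is to "determine whether the patient is meeting the goal set by the surgical team 4 hours after ketamine infusion". No volume, count or percent of goal is mentioned anywhere. The documents do not say what the goal consists of, whether it is common to all patients or set for each one, or what share of patients should reach it.

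On size and allocation: "One hundred subjects (50 in each arm) will be enrolled", and patients are "randomized to one of the two treatment group in a 1:1 ratio". The Statistical Analysis section names repeated-measures ANOVA as the main method and Mann-Whitney for non-normal data. It provides counts and percentages by category as description. It assigns no between-arm test specifically to spirometry.

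**The concern.** To judge whether a goal is met, the assessor has to set some achieved quantity against a target. As written, the plan keeps the judgement and drops both numbers. A patient just short of the goal and one far below it get the same score, as do a patient just over it and one well above. The threshold is set outside the study team and is not described, so a reader of the results could not tell what a given percentage meeting the goal means.

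At stake is a staff-assessed measure listed under aim 1. A moderate difference between arms in spirometry performance could go undetected because of how it was scored. A value not written down at 4 hours may not be recoverable later.

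**Working it through.** **Inputs from the documents.** 50 patients per arm, 1:1 allocation, type I error 0.05 (taken as two-sided), power 0.80, detectable difference 22.5%, SD 40% (Sample Size Justification). The SD and the difference refer to psychometric measures. They serve here only to supply an illustrative effect of 22.5/40 = 0.5625 SD.

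**Assumed inputs.** The quantity behind the goal is roughly normal with equal SDs, treatment shifts its mean, and a share p of patients meets the goal.

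**Step 1: the plan's own figure.** n per arm = 2 × [40 × (1.960 + 0.842)/22.5]² = 49.6, rounded up to 50. Power at 50 per arm is 0.803 by the normal formula and 0.795 by the t-test. The stated sample size reproduces.

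**Step 2: information kept by a yes/no cut.** Relative efficiency = φ(z)²/[p(1 − p)], where z is the normal quantile for p and φ is the normal density.

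- p = 0.50: 0.3989²/0.25 = 0.637
- p = 0.80 (or 0.20): 0.2800²/0.16 = 0.490
- p = 0.90 (or 0.10): 0.1755²/0.09 = 0.342

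The losses are 36%, 51% and 66%. At 5% or 95% the loss is 78%.

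**Step 3: what this means for power.** Place the two arms 0.5625 SD apart, symmetrically about the cut for p, so that the arm rates are Φ(z ± 0.28125). For two proportions, power = Φ{[|p₂ − p₁| − 1.96√(2p̄(1 − p̄)/n)] / √([p₁(1 − p₁) + p₂(1 − p₂)]/n)}, with n = 50.

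| Goal rate near | Arm rates | 50 per arm act like | Power of yes/no | n per arm for 80% |
|---|---|---|---|---|
| 50% | 38.9% vs 61.1% | 32 | 60% | 79 |
| 80% | 71.2% vs 86.9% | 25 | 49% | 105 |
| 90% | 84.1% vs 94.1% | 17 | 36% | 153 |

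The graded measure has about 80% power for the same shift. If p is instead the placebo rate and ketamine raises it, the formula gives 59%, 41% and 27% at placebo rates of 50%, 80% and 90%, but 55% and 44% at 20% and 10%. Power therefore depends on which side of one half the goal rate falls, as well as on its distance from it.

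**Step 4: the comparator matters.** Meeting the goal means that achieved value divided by goal is at least 100%, so the losses in step 2 are relative to percent of goal. If goals are set per patient and correlate with the achieved value (correlation r, assumed), the raw value carries extra between-patient variation. The yes/no score then keeps efficiency/(1 − r²) of the information in the unadjusted raw value. At r = 0.5 this is 0.637/0.75 = 85%, 0.490/0.75 = 65% and 0.342/0.75 = 46% for p = 0.50, 0.80 and 0.90. At r = 0.7 and p = 0.50 it is 0.637/0.51 = 125%, so yes/no would beat the raw value.

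**The case against.** A reader might infer more than the documents support, and several objections stand.

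- **A volume is being thrown away.** The documents never mention a spirometry volume or a device reading. The outcome is labelled as use, so the goal could be a frequency or a number of repetitions. What is certain is only that some achieved quantity is judged against a target.
- **Goals differ between patients, so equal performance is scored differently.** The text refers to the goal in the singular and does not say that it is individual. If it is common to all, this argument falls. If it varies, randomisation balances it on average, and the cost is noise rather than bias.
- **Most patients will meet the goal, giving a ceiling.** No expected rate is given, and a low rate is as possible as a high one.
- **Raw volume should be the outcome.** Step 4 shows that with individual goals the raw value may gain little or even do worse. A test with a set number of attempts would also be a new procedure and would move the measure from use towards effort-dependent performance.
- **The yes/no score is wrong because it does not fit repeated-measures ANOVA.** A single graded value at 4 hours does not fit that model either, so this is no argument for a graded outcome. It shows only that a test should be named.

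The outcome is also one of six secondary measures, and the sample size does not rest on it. None of this disposes of the narrower point: the whole outcome is one judgement against an undescribed threshold, and the numbers behind it are not kept.

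**Conclusion.** The point holds in limited form. The spirometry outcome is only goal met or not met, the goal has no stated unit or level, and no graded value is planned. The loss is about 36% at a 50% goal rate and about 66% at a 10% or 90% rate. These figures are not in the documents. They assume a roughly normal measure, a shift in mean and a goal rate in that range, and they apply against percent of goal rather than raw volume. It would be wrong to conclude that the trial is underpowered as a result: the stated 50 per arm reproduces for the psychometric measures and is untouched. This is a worthwhile, inexpensive improvement to a secondary outcome, not a flaw that threatens the primary conclusions.

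**What to change.** At the 4-hour assessment already planned, record the achieved value and the patient's goal, in whatever unit the surgical team's goal uses, and state that unit in the protocol. Make achieved value as a percent of goal the between-arm comparison. Name the test in advance: two-sample, or Mann-Whitney if the values are clearly non-normal. Keep goal met yes/no as a descriptive count and percentage by arm. Do not add a test with a fixed number of attempts, and do not make raw volume the main comparison.

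The cost is two numeric case report form fields and a line or two of text. The change depends on the goal being a numeric quantity that the assessor can read. If it is not, the yes/no score has to stay, and the protocol should then say what meeting the goal means and how the two proportions will be compared.

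### The serum outcomes are changes from a pre-operative sample that no planned analysis uses as a covariate, so the between-arm comparison may be less precise than it need be

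*Combined protocol and SAP*

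**What the plan says.** In the Outcome measures section the biomarker endpoints appear as "Exploratory secondary outcome measures: changes in serum levels of IL-1, IL6", followed by TNF-alpha and BDNF, "which will be collected at baseline (in the OR preoperatively), and 15 min and 4 hours after the termination of ketamine infusion". Under Overall study design and plan, treatment comes after the operation: "In the PACU, patients, if deemed medically stable by the study physician, will receive either 0.4mg/kg IV ketamine or placebo". No blood is planned between the end of surgery and the infusion.

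The same section introduces the blood sampling as "An additional component of the study, which is entirely optional" and gives no target number of donors. The ceiling is the whole trial: "One hundred subjects (50 in each arm) will be enrolled".

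The Statistical Analysis section, repeated in the Data Safety and Monitoring Plan, has no paragraph of its own for the serum markers. Its general method is: "Analysis of variance (ANOVA) test with repeated measures will be performed to determine within-patient effects (time) and between patient effects (treatment) on outcome measures". For non-normal data, "the Kruskal-Wallis test will be used for global significance, and Mann Whitney for subsequent pairwise comparisons". Baseline is not named as a covariate in either, and the text does not say which contrast tests treatment.

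**The concern.** A change score subtracts the whole baseline value, that is, it fixes the baseline coefficient at 1. This is efficient only when baseline predicts the later level with a slope close to 1. Here anaesthesia and abdominal surgery lie between the baseline draw and both later draws, so the relation may be weak. Subtraction then adds the baseline's own variability to the comparison and removes little in return. Covariate adjustment estimates the coefficient from the data instead.

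Naming repeated-measures ANOVA does not remove the problem. Its treatment-by-time contrast of the 15-minute or 4-hour draw against baseline is the same comparison as a between-arm test of change.

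Specific aim 2, meant to suggest a mechanism for ketamine, rests on these comparisons. What is at stake is how much information the trial extracts from samples it has already drawn and assayed.

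**Working it through.** **The plan's own figure.** The documents give no SD, correlation, effect size or power for any serum marker. The one sample-size figure is for the psychometric measures: a difference of 22.5% with SD 40%, alpha 0.05 and power 0.80. Two-sided, n = 2 × (1.96 + 0.84)² × (40/22.5)² ≈ 49.6, so 50 per arm, which reproduces. Power at 50 per arm is 0.803 by the normal approximation and 0.795 by the t-test.

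**Assumed inputs.** r is the correlation between the pre-operative and post-infusion levels, taken as 0.1 to 0.7. k is the post-infusion SD divided by the pre-operative SD, taken as 1 and 2. Donors per arm are taken as 25 and 50; only the upper limit of 50 comes from the protocol.

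**Formulas**, in units of the post-infusion variance:

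- change score: (k² + 1 − 2kr)/k², which is 2(1 − r) when k = 1
- level adjusted for baseline: 1 − r²
- level alone, ignoring baseline: 1
- excess of change over adjusted: (1/k − r)², which is never negative and is zero only when r = 1/k

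| r | k = 1: change | adjusted | adjusted/change | k = 2: change | adjusted | adjusted/change |
|---|---|---|---|---|---|---|
| 0.1 | 1.80 | 0.99 | 0.55 | 1.15 | 0.99 | 0.86 |
| 0.3 | 1.40 | 0.91 | 0.65 | 0.95 | 0.91 | 0.96 |
| 0.5 | 1.00 | 0.75 | 0.75 | 0.75 | 0.75 | 1.00 |
| 0.7 | 0.60 | 0.51 | 0.85 | 0.55 | 0.51 | 0.93 |

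With k = 1 the ratio simplifies to (1 − r²)/[2(1 − r)] = (1 + r)/2.

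**Change against ignoring baseline.** Change is the less precise of these two only when r < 1/(2k): below 0.5 with equal SDs, below 0.25 if the SD doubles. With equal SDs and r = 0.7, its variance is 0.60 of that for the level alone.

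**Power, for illustration only.** The standardised difference is 22.5/40 = 0.5625, borrowed from the psychometric calculation because there is none for serum. Two-sided t-test at 0.05, r = 0.3, change v adjusted (ignoring the one degree of freedom):

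- equal SDs: 0.38 v 0.53 with 25 per arm; 0.65 v 0.83 with 50 per arm
- SD doubled: 0.52 v 0.53 with 25 per arm

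**Simulation check** (equal SDs, 25 per arm, 4,000 runs). The standard errors for change, level alone and adjusted were 0.359, 0.283 and 0.280 at r = 0.2, and 0.220, 0.286 and 0.206 at r = 0.7. The mean estimate stayed within simulation error of the true value of zero for all three.

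**The case against.** The strongest reply is that the plan does not clearly commit to a two-sample test of change scores. The outcome is called a change, but no subtraction formula or test is attached to it. Specific aim 2 speaks of examining levels, and repeated-measures ANOVA would ordinarily take the level at each draw. This stands in part. A reader might infer that every serum comparison carries the baseline's noise, and the documents do not support that. The contrast of 15 minutes with 4 hours does not involve baseline. A treatment main effect averaged over all three draws is not a change score either; it has the different fault of shrinking a constant post-infusion effect to two thirds. What survives is that the outcome is defined as change, the contrasts against baseline are change comparisons, and no named method adjusts for baseline.

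Second, the disturbance that might lower the correlation might also widen the post-operative spread, and at k = 2 the loss is small or nil. This stands, so the equal-SD figures cannot be presented alone.

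Third, change across surgery is itself of interest: the Study Rationale asks whether marker levels alter with postoperative pain, separately from what ketamine does to them. This also stands. Reducing change to description would leave that question without an inferential analysis.

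Finally, the outcomes are exploratory and the sampling optional. That limits the consequence, but it is no reason to prefer the less precise comparison.

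**Conclusion.** The point holds as a minor one about efficiency. For the between-arm question, adjustment for the pre-operative level is at least as precise as the change score at any r and any SD ratio, apart from one degree of freedom. Over the assumed range of r, the adjusted variance is 0.55 to 0.85 of the change-score variance with equal SDs, and 0.86 to 1.00 if surgery doubles the SD. The documents supply neither r nor the SD ratio, so the actual loss could be substantial or close to nothing.

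Three stronger readings are not supported:

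- That nearly half the information is lost. This needs r near 0.1 and equal SDs together.
- That the serum sample is small. The protocol says only that giving blood is optional; anything up to 50 per arm is possible.
- That the comparison is biased. Baseline precedes treatment in a randomised trial, so the change and adjusted analyses estimate the same arm difference.

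**What to change.** In the Outcome measures section and in both copies of the Statistical Analysis text, state that the between-arm comparison for each marker is its level at 15 minutes and at 4 hours, each with the pre-operative level of the same marker as covariate, on the log scale if the values are skewed. This would also settle which serum contrast tests treatment.

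Keep within-patient change across surgery as a separate, named analysis for the Study Rationale's question of whether levels alter with postoperative pain. State the expected number of serum donors.

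The cost is a few sentences and one degree of freedom per comparison. No further samples, assays or patients are needed.
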